4.4.2 Phase 2 Northern Hemisphere

Approximately 500 participants will be randomized in a 3:3:3:1 ratio to receive either mRNA-1010 25 µg, mRNA-1010 50 µg, mRNA-1010 100 µg, , or a single dose of a licensed quadrivalent seasonal influenza vaccine (active comparator). Randomization to individual vaccination groups will proceed with parallel randomization among the 3 dose levels of mRNA-1010 (25, 50, and 100 µg total mRNA; vaccination groups 1 to 3) and the active comparator (vaccination group 4). Randomization will be stratified by age categories (18 to < 50 years, 50 to <65 years, or ≥ 65 years) and vaccination status in the previous flu season (received or not received).

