4.4.3 Phase 2 Extension

Approximately 200 participants will be randomly assigned in a 1:1:1:1 ratio to receive either mRNA-1010 6.25 µg, mRNA-1010 12.5 µg, mRNA-1010 25 µg, or licensed quadrivalent seasonal influenza vaccine (active comparator), with approximately 50 participants randomly assigned to each mRNA-1010 vaccination group and 50 participants to the Active Comparator Group. Randomization will be stratified by age (18 to < 50 years or ≥ 50 years), with at least 30% of participants in each dose group being ≥ 50 years of age.

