6.4.3 Phase 2 Northern Hemisphere and Phase 2 Extension

6.4.3.1 Primary Analysis of Immunogenicity Endpoints

Immune responses, as measured by GMT and seroconversion rate in the mRNA-1010 groups based on Day 29 anti-HA antibodies titers as measured by HAI assay, will be compared with that of participants receiving active comparator for all 4 strains.

For Phase 2 NH and Phase 2 Extension, the following evaluations will be performed at Day 29:

- An analysis of covariance (ANCOVA) model will be carried out with anti-HA antibodies titers at Day 29 as a dependent variable and vaccination group as an independent variable. This model will be adjusted for the baseline antibody titer. For Phase 2 NH, age group and vaccination status will be included as covariates. For Phase 2 Extension, age group will be included as a covariate. The GMT of vaccine-matched influenza A and B strains at Day 29 will be estimated by the geometric least square mean (GLSM) from the model (model-based GMT). The ratio of GMT (GMTr) will be estimated by the ratio of GLSM from the model. The corresponding 2 sided 95% CI will be provided to assess the difference in immune response between the mRNA 1010 compared with the active comparator at Day 29. The model will be conducted based on the log transformed values then back transformed to the original scale for presentation.
- The number and proportion of participants with seroconversion (defined in [Section 3.2.1](#)) at Day 29 will be provided with 2-sided 95% CI using Clopper Pearson method for each vaccination group. To compare the seroconversion rates between the vaccination groups, the Miettinen-Nurminen's method will be used to calculate the 95% CI for the difference in the seroconversion rates.

The analyses above may also be performed by vaccination status.

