6.4.3.2 Secondary Analysis of Immunogenicity Endpoints

- GMFR of vaccine-matched influenza A and B strains (as measured by HAI) at Day 29 with corresponding 95% CI using Clopper Pearson method for each vaccination group will be provided
- The number and proportion of participants with an anti-HA antibodies titer $\geq 1:40$ at Day 29 will be provided with 2-sided 95% CI using Clopper Pearson method for each vaccination group. The Miettinen-Nurminen's method will be used to

calculate the 95% CI of the difference in the rates of anti-HA antibodies titer $\geq 1:40$ at Day 29 between the vaccination groups.

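### Phase 2 seroconversion and titer ≥1:40 differences: the named confidence interval carries no strata, although the GMT ratio is adjusted for the randomisation factors; valid, but slightly wider than needed if the strata predict response

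*SAP*

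**What the plan says.** Randomisation in Phase 2 NH is stratified by three age classes and by vaccination in the previous influenza season, which makes six strata (SAP 4.4.2). In the Extension it is stratified by two age classes, "with at least 30% of participants in each dose group being" aged 50 or over (SAP 4.4.3).

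SAP 6.4.3.1 gives two primary immunogenicity comparisons with the active comparator:

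- **GMT ratio.** An ANCOVA on log titers with baseline titer in the model. The randomisation factors enter as well. The SAP's sentence on the first part reads "For Phase 2 NH, age group and vaccination status will be included as covariates"; the Extension model takes its one factor, age, in the same way.
- **Seroconversion difference.** Each group's rate gets a Clopper-Pearson interval. For the comparison, "the Miettinen-Nurminen's method will be used to calculate the 95% CI for the difference in the seroconversion rates".

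SAP 6.4.3.2 treats the difference in titer ≥1:40 the same way: "The Miettinen-Nurminen's method will be used to" obtain its 95% interval. Neither section names strata, weights or covariates for a rate difference. Protocol 9.5.3 asks only for the seroconversion difference with a 95% interval.

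SAP 6.1.2 and 6.1.3 provide displays by age group. For vaccination status in NH, 6.4.3.1 adds "The analyses above may also be performed by vaccination status". These are subgroup results; none gives an adjusted overall difference.

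**The concern.** The SAP already treats the randomisation factors as worth adjusting for. Protocol 9.5.3 gives the ANCOVA only a group term, and the SAP adds baseline titer and the strata. The binary comparison under the same heading was left crude, and no reason is given.

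Stratified randomisation balances the groups on the strata. If the strata predict response, an interval that ignores them still counts between-stratum variance that the design has largely removed, so it is wider than it need be. Each Phase 2 part has 3 doses × 4 strains = 12 seroconversion differences and another 12 for titer ≥1:40, all against a comparator group of 50. Only precision is at stake.

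**Working it through.** **The plan's own figures.** The SAP gives no width or precision for a rate difference. Its only design figures are the chances of seeing at least one AE, 1 − (1 − p)^n. They reproduce: 0.9006 and 0.9913 (n = 45; 5%, 10%), 0.9517 and 0.9896 (n = 150; 2%, 3%), 0.9231 and 0.9948 (n = 50; 5%, 10%). They do not bear on this point.

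**Inputs from the documents.** NH: 150 per dose against 50. Extension: 50 against 50. Six and two strata.

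**Assumed, because the documents are silent.** NH stratum sizes 39/36/18/21/12/24 per dose and 13/12/6/7/4/8 in the comparator (ages 18 to <50, 50 to <65, ≥65; within each, not vaccinated then vaccinated last season). Extension: 35/15 or 25/25 per group. Stratum response rates as shown below.

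**Step 1: large-sample ratio of standard errors.** With stratum shares q and rates p, ratio = √[p̄(1 − p̄) / Σ q p(1 − p)].

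- NH moderate (.70/.60/.55/.45/.40/.30): p̄ = 0.535, so √(0.2488/0.2294) = 1.042.
- NH strong (.85/.70/.55/.45/.35/.20): p̄ = 0.578, so √(0.2439/0.1917) = 1.128.
- In general, an excess e needs strata that explain 1 − 1/(1 + e)² of the response variance: about 9% of it for e = 5%, about 17% for e = 10%.

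**Step 2: simulation of the actual score intervals.** The stratified version weights stratum differences by w = n₁n₀/(n₁ + n₀). As a code check, 56/70 against 48/80 gives an unstratified interval of 0.0528 to 0.3382. NH results, 30,000 trials per scenario, true difference 0, percentages from unrounded widths:

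| Assumed stratum rates | Width after 10% exclusions, unstratified / stratified | Excess | Excess, exact balance | Unstratified coverage after exclusions |
|---|---|---|---|---|
| none (.50) | 0.328 / 0.328 | 0% | 0% | 95.0% |
| weak (.60 to .40) | 0.328 / 0.325 | 0.7% | 0.9% | 95.2% |
| moderate (.70 to .30) | 0.327 / 0.316 | 3.6% | 3.8% | 95.8% |
| extreme (.85 to .20) | 0.325 / 0.293 | 10.8% | 11.2% | 97.1% |

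Stratified coverage after exclusions was 94.8-95.0%. Per side, the moderate gain is (0.327 − 0.316)/2, about 0.6 points, and the extreme gain (0.325 − 0.293)/2 = 1.6 points.

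Extension after 10% exclusions, 30% aged ≥50 (younger/older rates): 0% (50/50), 1.4% (60/40), 3.5% (70/40), 8.6% (75/30). With an equal age split: 0%, 1.7%, 4.0%, 10.1%.

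**Step 3: sensitivity to the assumptions.** A separate set of simulations varied the strength of the strata and the overall rate:

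- Strong strata (NH: 30-point age span plus 30-point vaccination gap, or odds ratios 4 and 4; Extension: 40-point gap or odds ratio 5), overall rates 40-75%: 4.5% to 7.8%.
- Stronger still (NH: 40 plus 30 points, or odds ratios 6 and 4; Extension: 45 points or odds ratio 6): 5.4% to 10.3%. An odds ratio of 8 in the Extension gives 7.0% to 11.7%.
- NH with overall rates of 85-90%, even with strong strata: 0.9% to 2.0%.

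Widths of about 31-40 points apply only near 50% response. At 86-90% the NH widths are about 20-23 points.

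**Step 4: cost of stratifying.** Under exact 3:1 balance the weights are proportional to stratum size (3k·k/4k = 0.75k), so weighted and crude differences coincide. After 10% exclusions the mean gap is 0.3, 0.4, 0.7 and 1.0 points across the four NH scenarios (95th percentile 0.9, 1.2, 1.8, 2.6). The smallest assumed comparator stratum has 4 participants. The chance that fewer than 3 remain is 1 − 0.9⁴ − 4 × 0.9³ × 0.1 = 0.052, in line with the 4-6% of simulated trials in which strata had to be merged.

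**The case against.** The strongest reply is that nothing here is wrong. Both documents say that no formal hypothesis is tested, no margin uses the interval, and no passage promises a stratified rate difference. Adding covariates to one model does not oblige the other endpoint to match. Matching would in any case be incomplete, since the ANCOVA also adjusts for baseline titer and lists its factors without an interaction. The crude difference agrees with the group rates shown beside it and a weighted one may not. In the moderate NH case the 95th-percentile gap (1.8 points) exceeds the gain per side (0.6 points).

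All of this stands and limits the size of the point. It does not remove the gain: stratifying by the randomised groups kept coverage near nominal and gave a shorter interval when the strata matter, at almost no cost.

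Three stronger readings are tempting, and the documents do not support them:

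- *That the interval is invalid or under-covers.* It does not. Ignoring predictive strata makes it conservative.
- *That a loss near 10% is to be expected.* No stratum rates or sizes are given. About 11% in NH needs a 65-point spread between strata, and nothing shows that the strata predict response at all.
- *That a noninferiority conclusion hangs on the interval.* Protocol 4.2 mentions noninferior immunogenicity as the reason for the NH comparator, but no margin is set, and Protocol 9.2 and SAP 4.2 rule out formal hypotheses.

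The SAP also never calls the interval unstratified. That is the plain reading of its silence.

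**Conclusion.** The point holds as a small precision improvement, not an error. Under assumed stratum rates the interval is about 0-4% too wide for nil to moderate effects and roughly 5-10% for strong effects at mid-range rates. It reaches about 11% in the extreme 85%-to-20% case, and is about 1-2% or less at overall rates of 85-90%, as could apply to titer ≥1:40. If the strata do not predict response, nothing is lost by the present text except clarity about whether the interval is stratified.

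**What to change.** State in SAP 6.4.3.1 and 6.4.3.2:

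- The overall 95% CI for each rate difference uses the stratified Miettinen-Nurminen method with Cochran-Mantel-Haenszel weights, stratified by age group × previous-season vaccination status (NH) or by age group (Extension).
- If an NH stratum has fewer than 3 comparator participants in the analysis set, merge it with the adjacent age group within the same vaccination status: 18 to <50 with 50 to <65, and either older group with the other. If a stratum is still below 3, stratify by vaccination status only. In the Extension, a stratum below 3 leads to the unstratified interval.
- In by-age displays, stratify by vaccination status only (NH); in the Extension no factor remains, so the interval is unstratified. In by-vaccination-status displays, stratify by age group only. If a stratum is below 3 in any of these, use the unstratified interval.
- Report the overall unstratified interval as supportive, and footnote that the weighted difference may differ from the difference of the displayed crude rates.

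Cost: one SAP paragraph and one programming option, with no new data. The downsides are the sparse-stratum rule, whose threshold of 3 is a convention, and the gap from the crude difference, about 0.3-1.0 points on average under the NH assumptions above. The simulations merged only the two older age groups. In the assumed layout the 18 to <50 comparator strata hold 12 or 13, so the rule here would act almost identically.

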6.4.3.2 Secondary Analysis of Immunogenicity Endpoints

- GMFR of vaccine-matched influenza A and B strains (as measured by HAI) at Day 29 with corresponding 95% CI using Clopper Pearson method for each vaccination group will be provided
- The number and proportion of participants with an anti-HA antibodies titer $\geq 1:40$ at Day 29 will be provided with 2-sided 95% CI using Clopper Pearson method for each vaccination group. The Miettinen-Nurminen's method will be used to

calculate the 95% CI of the difference in the rates of anti-HA antibodies titer $\geq 1:40$ at Day 29 between the vaccination groups.

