IST	internal safety team
LLOQ	lower limit of quantification
MAAE	medically attended adverse event
max	maximum
MedDRA	Medical Dictionary for Regulatory Activities
min	minimum
MN	microneutralization
mRNA	messenger ribonucleic acid
NH	Northern Hemisphere

Abbreviation	Definition
NP	nasopharyngeal
PP	per-protocol
PT	preferred term
RT-PCR	reverse transcriptase polymerase chain reaction
SAE	serious adverse event
SAP	statistical analysis plan
SAS	Statistical Analysis System
SD	standard deviation
SoE	schedule of events
SOC	system organ class
TEAE	treatment-emergent adverse event
ULOQ	upper limit of quantification
WHO	World Health Organization
WHODrug Global	World Health Organization drug dictionary

1 Introduction

This statistical analysis plan (SAP), which describes the planned analyses for Study mRNA-1010-P101, is based on the most recent approved clinical study protocol (CSP), Amendment 4, dated 03-Feb-2022, and the most recent approved electronic case report form (eCRF), dated 01-Mar-2022.

In addition to the information presented in the statistical analysis plan section of the protocol (Section 9), which provides the principal features of analyses for this study, this SAP provides statistical analysis details/data derivations. It also documents modifications or additions to the analysis plan that are not “principal” in nature and result from information that was not available at the time of protocol finalization.

Study mRNA-1010-P101 is a Phase 1/2, randomized, stratified, observer-blind, dose-ranging study to evaluate the safety, reactogenicity, and immunogenicity of messenger ribonucleic acid (mRNA)-1010 seasonal influenza vaccine in healthy adults 18 years and older. Study design and analyses for Phase 1/2, and Phase 2 Northern Hemisphere, and Phase 2 Extension parts of the study will be described separately in the SAP, unless otherwise specified.

PPD Biostatistics and Programming team, designee of Moderna Biostatistics and Programming department, will perform the statistical analysis of the safety, reactogenicity, and immunogenicity data; Statistical Analysis System (SAS) Version 9.4 or higher will be used to generate all statistical outputs (tables, figures, listings, and datasets). The SAP will be finalized and approved prior to the primary analysis clinical database lock and treatment unblinding for the study. If the methods in this SAP differ from the methods described in the protocol, the SAP will prevail.

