3.2.2 Secondary Endpoints

The secondary objective will be evaluated by the following endpoints:

- The frequency of participants with anti-HA antibodies seroconversion as measured by HAI assay, and the frequency of participants with an anti-HA antibodies titer \geq 1:40 as measured by HAI assay at Day 29.
- GMFR of anti-HA antibodies comparing Day 29 to Day 1 (baseline) as measured by HAI assay.

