4.2 Statistical Hypotheses

No formal hypotheses will be tested for Phase 1/2, Phase 2 NH, and Phase 2 Extension.

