6.1.2 Phase 2 Northern Hemisphere

Age groups:

The following age groups will be used for summary purposes:

- Overall
- Age: ≥ 18 to < 50 years
- Age ≥ 50 to < 65 years
- Age ≥ 65 years

Vaccination status:

The following previous flu vaccination status may be used for summary purposes:

- Received season flu vaccine in the previous season
- Not received season flu vaccine in the previous season

Vaccination groups:

The following vaccination groups will be used for summary purposes:

- mRNA-1010 25 µg
- mRNA-1010 50 µg
- mRNA-1010 100 µg
- Active comparator

For Phase 2 NH, all analyses and data summaries/displays will be provided by vaccination group (and then by age group) using appropriate analysis population, unless otherwise specified. Summaries may also contain a display for all mRNA-1010 vaccination groups (Total mRNA-1010 group) or all vaccination groups, including active comparator (Overall group). Additional summaries/displays based on vaccination status will be provided for immunogenicity analyses only.

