6.1.3 Phase 2 Extension

Age groups:

The following age groups will be used for summary purposes:

- Overall
- Age: ≥ 18 to < 50 years
- Age ≥ 50 years

Vaccination groups:

The following vaccination groups will be used for summary purposes:

- mRNA-1010 6.25 µg
- mRNA-1010 12.5 µg
- mRNA-1010 25 µg
- Active comparator

For Phase 2 Extension, all analyses and data summaries/displays will be provided by vaccination group (and then by age group) using appropriate analysis population, unless otherwise specified. Summaries may also contain a display for all mRNA-1010 vaccination groups (Total mRNA-1010 group) or all vaccination groups, including active comparator (Overall group).

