6.4 Immunogenicity Analysis

The following description of immunogenicity analyses will be applied to Phase 1/2, Phase 2 NH, and Phase 2 Extension. Phase 2 NH and Phase 2 Extension will share the same analyses, unless otherwise specified.

The analyses of immunogenicity will be based on the PP Set and will be performed by vaccination group as defined in [Section 6.1](#). If the number of participants in the FAS and PP Set differs (defined as the difference divided by the total number of participants in the PP Set) by more than 10% for each age group, supportive analyses of immunogenicity may be conducted using the FAS. The supportive analysis is required if the condition is met.

The GMT and geometric mean (GM) level will be calculated using the following formula:

$$2^{\left\{ \frac{\sum_{i=1}^n \log_2(t_i)}{n} \right\}}$$

where t_1, t_2, \dots, t_n are n observed immunogenicity titers or levels.

The GMFR measures the changes in immunogenicity titers or levels within participants. The GMFR will be calculated using the following formula:

$$2^{\left\{ \frac{\sum_{i=1}^n \log_2(v_{ij}/v_{ik})}{n} \right\}} = 2^{\left\{ \frac{\sum_{i=1}^n \log_2(v_{ij}) - \log_2(v_{ik})}{n} \right\}}$$

where, for n participants, v_{ij} and v_{ik} are observed immunogenicity titers or levels for participant i at time points j and k , $j \neq k$.

The 95% CIs for GMT and GMFR will be calculated based on the t distribution of the log-transformed values then back transformed to the original scale for presentation, unless otherwise specified.

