6.4.2.3 Exploratory Analysis of Immunogenicity

The below exploratory analyses of immunogenicity may be performed:

- GMT of vaccine-mismatched strain-specific anti-HA antibodies with corresponding 95% CI will be provided at each time point using methods described in [Section 6.4](#).
- GMFR of vaccine-mismatched strain-specific anti-HA antibodies with corresponding 95% CI will be provided at each post-baseline time point over pre-injection baseline at Day 1 using methods described in [Section 6.4](#).
- Descriptive summaries of virus-specific T-cell and B-cell responses measured by flow cytometry or other methods as well as targeted repertoire analysis of B cells and T cells after vaccination.
- Descriptive summaries of immunologic endpoints to further characterize antibody responses.
- The number of participants with confirmed influenza infection by RT-PCR test.
- Listing of immune response of participants infected by influenza

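### SAP 6.4.3.2 prescribes a binomial (Clopper-Pearson) interval for the Day 29 geometric mean fold rise in Phase 2, which cannot be computed

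*SAP*

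**What the plan says.** The Day 29 fold rise is a named Phase 2 secondary endpoint. SAP 3.2.2 lists "GMFR of anti-HA antibodies comparing Day 29 to Day 1 (baseline) as measured by HAI assay".

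Two places in the SAP set its confidence interval:

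- SAP 6.4, which covers all three study parts, defines the GMFR as 2 raised to the mean of the log2 titer ratios and states: "The 95% CIs for GMT and GMFR will be calculated based on the t distribution of the log-transformed values". The limits are then back-transformed. The sentence closes with an exception for cases where another method is specified.
- SAP 6.4.3.2, which covers Phase 2 NH and Phase 2 Extension, plans, group by group, "GMFR of vaccine-matched influenza A and B strains (as measured by HAI) at Day 29 with corresponding 95% CI using Clopper Pearson method".

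The next bullet of 6.4.3.2 applies the same method to the proportion with a titer of at least 1:40, where it is appropriate.

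Protocol 9.5.3 promises a GMFR with a 95% CI for Phase 2 NH. The sentence before it describes t-based intervals on log values, but that sentence follows the GMT statement, so whether it also covers the GMFR is open to reading. The protocol's Phase 2 Extension paragraph does not mention the GMFR. SAP Section 1 adds: "If the methods in this SAP differ from the methods described in the protocol, the SAP will prevail". SAP Section 7 reports no changes from the protocol's planned analyses.

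**The concern.** Clopper-Pearson is an exact interval for a binomial proportion. A geometric mean fold rise is a continuous quantity on the log scale, so the named method does not apply to it.

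The general rule in SAP 6.4 would normally supply the interval, but it yields to a specific instruction, and 6.4.3.2 is one. Read literally, the valid rule is switched off for this endpoint and replaced by one that cannot be run. The programmer must then either depart from the SAP without a documented basis or raise a query. The only count that could be formed from the fold rises is the number of participants above some threshold. That is a different quantity, close to the seroconversion rate already reported.

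**Working it through.** The plan states no GMFR value, standard deviation or interval, so there is no figure of its own to reproduce. The check is whether each named method can produce an interval for this statistic.

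**Inputs.** From SAP Table 1, Phase 2 NH has three mRNA-1010 groups of 150 and a comparator group of 50, and the Extension has four groups of 50. There are four strains. From SAP 6.4, GMFR = 2^[(1/n) Σ log2(Day 29 titer / Day 1 titer)].

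**1. Clopper-Pearson.** For x successes out of n, with x an integer from 0 to n, the limits are

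- lower = Beta(0.025; x, n − x + 1)
- upper = Beta(0.975; x + 1, n − x)

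with the lower limit set to 0 at x = 0 and the upper limit set to 1 at x = n. At n = 50:

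- x = 0 gives 0 to 0.071
- x = 25 gives 0.355 to 0.645
- x = 50 gives 0.929 to 1

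Every result lies between 0 and 1.

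**2. Applying it to the GMFR.** The definition supplies no x. Forcing an assumed GMFR of 4 in as a proportion needs x = 4 × 50 = 200 out of 50. The beta parameters n − x + 1 and n − x are then −149 and −150. At n = 150, x = 600 and they are −449 and −450. Beta parameters must be positive, so both limits are undefined in each case.

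**3. The method of SAP 6.4.** The interval is the GMFR divided and multiplied by 2^h, with h = t(0.975; n − 1) × SD / √n, where SD is that of the log2 fold rise. The documents give no SD, so a range is assumed:

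| Assumed SD (log2) | Factor, n = 50 | Factor, n = 150 |
|---|---|---|
| 1.0 | 1.22 | 1.12 |
| 1.5 | 1.34 | 1.18 |
| 2.0 | 1.48 | 1.25 |

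With an assumed GMFR of 4 and SD of 1.5, the interval is 2.98 to 5.38 at n = 50 and 3.38 to 4.73 at n = 150. This method works in every case tried.

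**4. Reach of the phrase.**

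- Overall: 4 strains × 4 groups × 2 parts = 32 intervals.
- With the by-age displays required by SAP 6.1.2 and 6.1.3: NH (overall + 3 age groups) × 4 × 4 = 64, and Extension (overall + 2 age groups) × 4 × 4 = 48. The total is 64 + 48 = 112.

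Pooled columns, displays by prior vaccination status and supportive FAS analyses could add more, but the SAP does not fix their number for this endpoint.

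**5. Use elsewhere in the SAP.** Clopper-Pearson is otherwise named only for proportions: solicited reactions (6.3.2), seroconversion (6.4.2.1, 6.4.2.2, 6.4.3.1) and titer of at least 1:40 (6.4.3.2). The Phase 1/2 GMFR bullets in 6.4.2.1 and 6.4.2.2 name no special method and so take the t-based rule. The GMFR bullet in 6.4.3.2 is the one exception.

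**The case against.** The strongest reply is that this is a copying slip with the right rule in the parent section. SAP 6.4 names the GMFR and applies expressly to both Phase 2 parts. The override cannot be executed, the adjacent bullet shows where the phrase came from, and SAP Section 7 indicates that no new method was intended. A competent programmer would return to Section 6.4. Because the named method fails on non-count data, it is unlikely to produce a wrong number unnoticed.

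Most of that stands, and it limits the consequence. It does not make the instruction correct: Section 6.4 gives way to a specific rule by its own terms, and 6.4.3.2 contains one.

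Three narrower points also stand:

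- The SAP-prevails clause settles differences between SAP and protocol. The conflict here is inside the SAP, so the clause only means the protocol cannot be relied on as a fallback.
- The protocol's t-based sentence for Phase 2 NH may have been meant to cover the GMFR. Even so, it says nothing for the Extension.
- The exploratory bullet in SAP 6.4.2.3, which gives a GMFR interval "at each post-baseline time point over pre-injection baseline at Day 1 using methods described in" Section 6.4, concerns Phase 1/2 and mismatched strains. It shows the SAP's usual practice but does not itself contradict the Phase 2 instruction.

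**Conclusion.** The concern holds. The interval method that SAP 6.4.3.2 assigns to the Day 29 GMFR cannot be computed for that statistic, and as written it overrides the valid method in SAP 6.4. It affects 32 overall intervals, or 112 if the age-group displays are produced for this endpoint as SAP 6.1.2 and 6.1.3 require. Those counts show reach and are not a measure of bias.

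The consequence is limited. SAP 4.2 states "No formal hypotheses will be tested for Phase 1/2, Phase 2 NH, and Phase 2 Extension". The GMFR point estimates, the ANCOVA ratio of GMTs, the seroconversion difference and the sample size are all unaffected. The conclusion follows from the definitions alone. The assumed GMFR and SD values serve only to illustrate that the t-based interval works. The text should be corrected because it is an operative rule for a named secondary endpoint.

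**What to change.** In the GMFR bullet of SAP 6.4.3.2, delete the reference to Clopper-Pearson and state that the 95% CI is calculated from the t distribution of the log-transformed fold rise and back-transformed, as in Section 6.4. Keep Clopper-Pearson for proportions only: seroconversion, titer of at least 1:40, and solicited adverse reactions. Make the change before database lock, including any lock taken to support a Day 29 interim report, so that the method is on record before the results are seen.

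The cost is one phrase in the SAP. Data collection, sample size and all other analyses stay the same.
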